### **1.2 Chemotherapy-associated toxicities**

We will examine differences in chemotherapy tolerance through patient-reported outcomes. The NCI Patient-Reported Outcomes-Common Terminology Criteria for Adverse Events (PRO-CTCAE) is a patient-reported outcome measurement system developed to characterize the frequency, severity, and interference of symptomatic treatment toxicities. Participants completed a customized 9-item PRO-CTCAE questionnaire around the initiation of each chemotherapy cycle reporting on the following symptomatic toxicities: nausea, vomiting, diarrhea, shortness of breath, hand-foot syndrome, numbness in hands and feet, pain, muscle aches and fatigue. Each symptom had 1-3 questions that asked about frequency and/or severity, and/or interference. Answers from those questions were then categorized as none, mild, moderate, or severe, based on expert consensus of oncologists [1].

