All 4 adjuvant therapy regimens have potential for multiple toxicities, including but not limited to gastrointestinal (e.g. nausea, emesis, diarrhea, abdominal cramping or discomfort), bone

marrow suppression (i.e. lowering white blood cells and thus immune system or platelets increasing bleeding risk), and fatigue and anorexia symptoms (Table 1). Oxaliplatin can lead to cold-induced and/or cumulative peripheral neuropathy, manifested as numbness, pins and needles, or pain in hands and feet, which can impact function.

1.4 Pharmacokinetics of 5-FU and oxaliplatin are altered by body composition:

Cytotoxic agents, such as fluoropyrimidine and oxaliplatin, are considered narrow therapeutic index drugs, where small changes in drug exposure can greatly impact clinical efficacy and toxicity. 5-FU is hydrophilic, but widely distributed through active transport¹². It undergoes extensive metabolism, primarily through dihydropyrimidine dehydrogenase (DPYD), variants of which have been associated with increased risk of toxicity to 5-FU¹³. On the basis of these considerations, 5-FU clearance (CL) and volume of distribution (V) are likely related to body composition. Gusella *et al.* studied the PK of adjuvant 5-FU (425 mg/m² IV bolus) in 34 colorectal cancer patients¹⁴ and determined that CL was significantly correlated with sex and fat free mass (FFM), while V was correlated with sex and Total Body Water (TBW). Overall, they concluded that CL of 5-FU was better predicted by FFM and TBW than by Body Surface Area (BSA)¹⁴. Thus, clearance of 5-FU is expected to increase (i.e. exposure decrease) in individuals with a higher FFM.

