4. STUDY MEASUREMENTS

Initial screening will take place via telephone. At the in-person baseline visit, after the patient signs the consent form, s/he will undergo a series of baseline assessments, questionnaires and blood draws as described above. Many of the data collection instruments will be either data entered by a researcher or self-administered by participants into REDCap, which is a secure web application for managing online surveys and databases. The table below provides an overview of the measurements that participants will undergo over the course of the protocol and the timing of these measurements:

Table 7. Measurement Schedule

Measure	Screening	Baseline	Weekly	PK Cohort Only	Post-Intervention Visit ³
Phone screening questions- PA screening and additional questions	X				
PAR-Q	X				
SF-36 ⁴		X			X
Demographics ⁴		X			
Paffenbarger questionnaire		X			X
Physical function tests (balance, gait speed, sit and stand, grip strength)		X			X
Food frequency questionnaire ⁴		X			X
Height, weight, waist and hip circumference		X			X
Whole body DXA		X		X ²	X
Patient-completed side effects questionnaires ⁴		X			X
D3- creatine dilution		X			X
NCI PRO CTCAE			X ¹		
Medical record review for chemotherapy dosing and toxicities			X		
Physical activity and nutrition logs			X		
Inflammatory markers		X			X
Pharmacokinetics (PK)				See section 4.14	
Injury history questionnaire ⁴					X
Intervention follow-up survey					X

¹ At each scheduled intervention visit (for intervention arm) and thereafter by phone or secure web-link every time chemotherapy appointment is scheduled. For U group controls, an RA will administer by phone or secure web-link every time a chemotherapy appointment is scheduled.

² For PK cohort, a DXA scan will also occur at time of 2nd PK draw, at approximately 4 months after initiation of the intervention

³ To be conducted within 2 weeks after last cycle of chemotherapy and end of intervention

⁴ As a result of COVID-19, to reduce in person time participants will complete baseline and post-intervention questionnaires virtually. Study staff will email participants a secure web-link, send them home with paper copies to be mailed back within 3 days, or administer questionnaires over the phone.

4.1 Screening questionnaire:

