At the initiation of adjuvant chemotherapy, we will ascertain planned treatment course for participants, including planned cumulative dose and planned treatment duration. We will then examine the EMR for changes in chemotherapy dose and timing. The following variables will be defined for each drug administered:

- Planned dose intensity (mg/week) = planned total dose / planned duration of therapy (weeks)
- Actual dose intensity (mg/week) = actual total dose (mg) / actual duration of therapy (weeks)
- Relative dose intensity (RDI) (%) = actual total dose intensity / planned total dose intensity
- Average relative dose intensity (ARDI) (%) = the average across all regimens of the relative dose intensity
- Number of cycles of chemotherapy and date of initiation of each cycle

In addition, we will report on early stoppage by calculating actual number of cycles / planned number of cycles of adjuvant therapy. We will only consider dose reductions that occur after start of intervention. Chemotherapy treatment forms will be used to capture data from the EMR on chemotherapy administration (see Appendix 13.7.4). A researcher will record all relevant chemotherapy treatment variables in an online REDCap form.

4.12 Chemotoxicity:

Total combined number of moderate and severe chemotherapy-associated toxicities, assessed via medical record review, patient-completed NCI PRO-CTCAE and patient-completed side effects questionnaires. As shown in the Appendix, we will use a series of validated questionnaires for chemotherapy-associated side effects including NCI PRO-CTCAE and a questionnaire on neurotoxicity utilized in a recent phase III trial with oxaliplatin⁴⁸. See Appendix 13.7. Throughout the intervention, the research manager or assistant will email a secure web-link to the patient requesting completion of the NCI PRO-CTCAE questionnaire in advance of his/her next chemotherapy infusion visit. A researcher will record all relevant chemotoxicity variables in an online REDCap form. Participants will complete the patient-completed side effects questionnaire and NCI PRO-CTCAE questionnaire in online REDCap surveys.

4.13 Inflammatory blood measures:

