### **2.2 Analysis of primary endpoints**

## Statistical Analysis Plan

FORCE: Focus on Reducing Dose-Limiting Toxicities in Colon Cancer with Resistance Exercise

All data analyses will be by intent-to-treat. Multiple linear regression will be used to assess the difference between the RT and UC groups in RDI. We will analyze RDI individually for each drug and then across all chemotherapy regimens combined. We will use logistic regression to examine the commonly used cut points < 85% and <70% RDI as outcomes.

We will assess the difference between RT and UC groups in self-reported treatment toxicities in three ways:

- A. as a binary variable with yes as the occurrence of any of one of 8 symptoms that are reported as moderate or severe over the course of chemotherapy in RT vs. UC. We will exclude the PRO-CTCAE muscle ache item from the composite score (will be reported separately), since that is believed to be related to the performance of the resistance training intervention. We'll utilize logistic regression for point and interval estimation of odds ratios, RT vs. UC, for any (i.e., one or more) of 8 symptoms reported as moderate severe, for each symptom individually, and finally in groups of similar symptoms, such as gastrointestinal issues;
- B. as the number of the 8 symptoms reported as moderate or severe at least once over the course of chemotherapy in RT v. UC (a count ranging from 0-8). We will use Poisson regression with allowance for overdispersion for point and interval estimation of relative differences (rate ratio) in the mean total number of moderate or severe toxicities reported at least once over the course of chemotherapy; and
- C. as longitudinal analyses of number of moderate or severe toxicities reported per cycle in relation to randomization arm (RT vs. UC) and time since randomization using Poisson regression with allowance for overdispersion. Generalized estimation equations (GEE) will be used for model parameter estimation to account for within person correlation in repeated measures. The main effect for randomization arm is interpreted as the average treatment effect over the time. Heterogeneity in effect over time will be assessed by inclusion of randomization arm by time-interaction terms.

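### The PRO-CTCAE toxicity endpoint has no scheduled control-arm report after the final planned cycle begins, and the SAP does not say which reports count

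*SAP*

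**What the plan says.** SAP 1.2 approaches tolerance through patient reports, and PRO-CTCAE is the only instrument it describes: "Participants completed a customized 9-item PRO-CTCAE questionnaire around the initiation of each chemotherapy cycle". SAP 2.2 then analyses eight of the nine symptoms. A is a yes/no version. B is defined "as the number of the 8 symptoms reported as moderate or severe at least once over the course of chemotherapy in RT v. UC". C models the count per cycle against arm and time since randomization. None of the three names a first or last report to be counted, and neither document gives a recall period.

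Protocol 4.12 has staff send a link "requesting completion of the NCI PRO-CTCAE questionnaire in advance of his/her next chemotherapy infusion visit". Table 7 footnote 1 sets the schedule by arm. For RT it reads "At each scheduled intervention visit (for intervention arm) and thereafter by phone or secure web-link every time chemotherapy appointment is scheduled". For controls it reads "For U group controls, an RA will administer by phone or secure web-link every time a chemotherapy appointment is scheduled". The PRO-CTCAE row carries only that footnoted mark, with nothing under Baseline or Post-Intervention.

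A post-intervention visit does take place. Footnote 3 says "To be conducted within 2 weeks after last cycle of chemotherapy and end of intervention", and the row "Patient-completed side effects questionnaires" is marked there. Protocol 4.12 names three toxicity sources: record review, PRO-CTCAE and the side effects questionnaires. The SAP analyses use only the second.

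The other primary endpoint is anchored in time. SAP 1.1 starts RDI at the first post-randomization cycle, and Protocol 4.11 ignores dose reductions made before the intervention starts. Protocol 3.7 allows entry up to the third infusion and expects most baseline visits at the first or second.

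**The concern.** There are three linked problems.

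- **End of treatment.** A form completed around the start of the last cycle cannot report what develops later in that cycle. That cycle has the longest exposure to exercise. It also carries the highest cumulative dose, which matters for neuropathy: "Oxaliplatin can lead to cold-induced and/or cumulative peripheral neuropathy".
- **Difference between arms.** RT patients also report at intervention visits and controls do not. In outcomes of the at-least-once kind, an extra reporting occasion in one arm can only raise that arm's count.
- **Start of treatment.** In A and B a single moderate report settles the matter: it makes the patient a yes in A and adds the symptom to B, whatever happens afterwards. If that report concerns a cycle given before exercise, it records toxicity that the intervention could not have changed.

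**Working it through.** **The plan's own figure.** Protocol 9.3.4 states power 0.80 for a difference of 0.42 SD, two-sided alpha 0.05, with 90 per arm (SAP 2.1). A two-sample t-test gives 0.800, and 0.42 × 17.3 = 7.27 against the stated 7.3. These figures reproduce, and nothing below changes them.

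**Step 1: cycles followed by a later form.** Inputs are the planned cycles C from Table 3 and the infusion s at which the intervention starts (1 to 3, Protocol 3.7). On-intervention cycles number C − s + 1. Forms tied to infusions s + 1 to C follow cycles s to C − 1, so C − s of those cycles have a later form. Coverage is (C − s)/(C − s + 1), assuming the full course is given and no form is completed after the last infusion.

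| Regimen | C | s = 1 | s = 2 | s = 3 |
|---|---|---|---|---|
| 6-month FOLFOX | 12 | 11/12 | 10/11 | 9/10 |
| 6-month CAPOX | 8 | 7/8 | 6/7 | 5/6 |
| 3-month FOLFOX | 6 | 5/6 | 4/5 | 3/4 |
| 3-month CAPOX | 4 | 3/4 | 2/3 | 1/2 |

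The uncovered share, 1/(C − s + 1), is 8–10% for 6-month FOLFOX, 12–17% for 6-month CAPOX, 17–25% for 3-month FOLFOX and 25–50% for 3-month CAPOX. One form after the last cycle would bring every cell to full coverage.

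**Step 2: can RT patients report after the last infusion?** Table 6 gives 4–6 exercise sessions, every 2–3 weeks. For 3-month CAPOX (4 cycles of 21 days) infusions fall in weeks 1, 4, 7 and 10. With a start at the third infusion (week 7) and two-week spacing, sessions fall in weeks 7, 9 and 11. The week 11 session follows the last infusion, and the SAP's introduction continues the intervention beyond the last cycle. Footnote 1 gives controls no matching occasion.

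**Step 3: effect of one pre-exercise report.** This step needs three assumptions that the documents do not state: each form describes the preceding cycle, control-arm rates are equal across cycles, and the true rate ratio is R in exposed cycles and 1 before exercise. With k counted forms, of which the first describes a pre-exercise cycle, the average ratio is (1 + (k − 1)R)/k. Entry at the third infusion gives k = C − 2. For an assumed R = 0.70:

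- k = 2 (3-month CAPOX): (1 + 0.70)/2 = 0.85
- k = 4 (3-month FOLFOX): (1 + 2.10)/4 = 0.775
- k = 6 (6-month CAPOX): (1 + 3.50)/6 = 0.75
- k = 10 (6-month FOLFOX): (1 + 6.30)/10 = 0.73

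For R from 0.60 to 0.80 the average runs from 0.80 to 0.90 at k = 2 and from 0.64 to 0.82 at k = 10. This applies to a per-cycle analysis such as C. It does not translate directly to A or B.

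**The case against.** The case on the other side has real force.

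- **Other sources cover the period.** The side effects questionnaires are given at the post-intervention visit, record review runs throughout, and Protocol 4.12 names a dedicated oxaliplatin neurotoxicity questionnaire. A reader might infer that toxicity of the last cycle is never measured. The documents do not support that. What stands is that these sources do not enter analyses A to C.
- **Early stoppers.** A reader might infer that the cycle that led a patient to stop is always unreported and that dose-limiting toxicity is hidden. The trigger is a scheduled appointment and the link goes out beforehand, so a patient who stops with an appointment booked may still report. RDI also captures early stoppage directly. What remains is that the plan does not guarantee a report.
- **Recall.** No recall period is stated, and the SAP says around, not before, the start of a cycle. The argument about pre-exercise cycles is therefore conditional. The end-of-treatment gap depends on it much less, since a form near the start of a cycle can cover at most its first days.
- **Entry time.** Baseline is expected mostly at the first or second infusion, and a patient starting at the first has no earlier cycle. A coverage of one half applies only to 3-month CAPOX with the latest entry.
- **Persistence.** In A and B a symptom already reported stays counted, so losing one form need not change the result. Missing the last cycle in both arms dilutes the effect only if benefit grows with exposure, which is not shown.
- **The Weekly column.** The Table 7 mark sits under Weekly, which read alone would cover the last cycle. Footnote 1, Protocol 4.12 and SAP 1.2 all define a schedule by appointment or cycle instead.

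**Conclusion.** The point holds for the SAP's PRO-CTCAE endpoint, not for toxicity measurement in the trial as a whole. Two parts rest on the text. First, controls have no scheduled PRO-CTCAE after the last planned infusion, while RT patients may have one. Second, A and B have no defined counting window, although RDI has one. C includes time since randomization but does not say which reports are in.

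The part about pre-exercise cycles rests on look-back recall and on entry at the second or third infusion. The size depends on regimen and entry time: small for 12-cycle regimens (1 cycle in 10 to 12 uncovered) and material for 3-month regimens (1 in 4 to 6 for FOLFOX, 1 in 2 to 4 for CAPOX). The documents do not give the regimen mix, so no overall figure can be derived. The stated sample size and power are unaffected. This should be corrected, mainly through SAP wording.

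**What to change.** 1. **If collection is still open:** mark PRO-CTCAE at the post-intervention visit in Table 7 for both arms, including patients who stop early. The cost is one short form at a visit that already includes questionnaires. The SAP describes randomization and form completion in the past tense, so this may no longer be possible.
2. **In SAP 2.2, with data already collected:** state the recall period and attribute each report to the cycle it describes. In A, B and C, count only reports on cycles given after randomization, and only from a report schedule common to both arms. Use an earlier report as a baseline covariate only if it was completed before randomization. A later one is a self-report from a patient who may already know the arm, and adjusting for it could introduce bias.
3. **If collection has ended:** state that PRO-CTCAE does not cover the final cycle, and use the post-intervention side effects questionnaire and record review as a sensitivity analysis.

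Items 2 and 3 cost SAP wording and some programming. The downsides are slightly fewer counted reports and a missing baseline report for some patients, since Table 7 schedules no PRO-CTCAE at baseline.

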## **STATISTICAL CONSIDERATIONS**

### **2.1 Sample Size**

This study intended to randomize 180 colon cancer patients, with 90 in each treatment arm. In the end, due to missing data due to COVID, we randomized 183 participants, 92 to RT and 91 to UC. We expect chemotherapy dosing and completion rates (RDI, ARDI) to be assessed on all participants.

### **2.2 Analysis of primary endpoints**

## Statistical Analysis Plan

FORCE: Focus on Reducing Dose-Limiting Toxicities in Colon Cancer with Resistance Exercise

All data analyses will be by intent-to-treat. Multiple linear regression will be used to assess the difference between the RT and UC groups in RDI. We will analyze RDI individually for each drug and then across all chemotherapy regimens combined. We will use logistic regression to examine the commonly used cut points < 85% and <70% RDI as outcomes.

We will assess the difference between RT and UC groups in self-reported treatment toxicities in three ways:

- A. as a binary variable with yes as the occurrence of any of one of 8 symptoms that are reported as moderate or severe over the course of chemotherapy in RT vs. UC. We will exclude the PRO-CTCAE muscle ache item from the composite score (will be reported separately), since that is believed to be related to the performance of the resistance training intervention. We'll utilize logistic regression for point and interval estimation of odds ratios, RT vs. UC, for any (i.e., one or more) of 8 symptoms reported as moderate severe, for each symptom individually, and finally in groups of similar symptoms, such as gastrointestinal issues;
- B. as the number of the 8 symptoms reported as moderate or severe at least once over the course of chemotherapy in RT v. UC (a count ranging from 0-8). We will use Poisson regression with allowance for overdispersion for point and interval estimation of relative differences (rate ratio) in the mean total number of moderate or severe toxicities reported at least once over the course of chemotherapy; and
- C. as longitudinal analyses of number of moderate or severe toxicities reported per cycle in relation to randomization arm (RT vs. UC) and time since randomization using Poisson regression with allowance for overdispersion. Generalized estimation equations (GEE) will be used for model parameter estimation to account for within person correlation in repeated measures. The main effect for randomization arm is interpreted as the average treatment effect over the time. Heterogeneity in effect over time will be assessed by inclusion of randomization arm by time-interaction terms.

In addition to treatment arm, each model will include covariates used in the randomization procedure (study site, treatment duration, treatment regimen, gender, stage). Exploratory analyses will examine the impact of including additional (not pre-specified) covariates in estimation of treatment effect, with a focus on variables with chance imbalance in distributions by treatment group. Analyses resulting in an appreciable change in the estimate of between-group differences or increase in precision of the treatment effect will be noted.

We will also conduct analyses stratified by sex, frailty status and duration of the intervention, excluding the strata-variable from the covariate list (i.e., exclude gender in analysis by men and women) by inclusion of appropriate cross product terms in regression models. Exploratory analyses will additionally assess heterogeneity in treatment effect on study outcomes by exercise adherence.

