set of potential confounders for cross-sectional analyses at baseline includes age, sex, body mass index or weight, race/ethnicity and tumor stage. For longitudinal analyses, potential confounders also include chemotherapy type, intervention assignment and time from surgery and/or chemotherapy start to assessment. We will include those covariates resulting in a 10% or more change in the d3 creatine muscle mass regression coefficient. The change-in-estimate approach to confounder selection performs well with regard to power, bias, mean squared error and confidence interval coverage.

9.3.4 Power:

Given previous exercise studies in cancer patients, we assume approximately 10% drop out with no follow-up DXA and blood draw for biomarker assessment. We expect chemotoxicity metrics (RDI, # toxicities) to be assessed on the full sample. We have sufficient power (.80) to detect a between arm difference in means of at least .42 standard deviation (s.d.) units (two-sided t-test, $\alpha=.05$) in Aim 1 analyses of chemotoxicity. With an expected RDI s.d. of 17.3⁴⁵, the minimum detectable difference in mean RDI is 7.3%, which is clinically meaningful and similar to effects found with a study of exercise among breast cancer patients receiving adjuvant chemotherapy⁴⁵. With the expected loss to follow-up and reduced sample size of 81 per group, the minimum detectable between arm difference in mean change is .44 units, which is considered in the “small” to “medium” range in effect size using the terminology and classification of Cohen. Relevant to Aim 4, on pharmacokinetics, a sample size of 30 subjects will provide sufficient power (.80) to detect a mean change of at least 0.5 s.d. units (two-sided t-test, $\alpha=.05$). Given previous data²⁶, the minimum detectable change in clearance of oxaliplatin or 5-FU due to RT is 15%.

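### Many analyses are listed as primary, none is named as the deciding one, and no multiplicity rule appears in the visible text

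*SAP*

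**What the plan says.** The protocol's primary objective (section 2.1) joins chemotherapy dosing and chemotherapy toxicity in one sentence and does not rank them. Protocol section 9.3.1 gives mean RDI for each agent, mean average RDI (ARDI) and a Poisson model for the number of grade 3 and 4 toxicities, again unranked.

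The SAP keeps both domains as primary (sections 1.1 and 1.2). Section 2.2 then sets out the analyses:

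- **Dosing:** "We will analyze RDI individually for each drug and then across all chemotherapy regimens combined", plus logistic models for the "commonly used cut points < 85% and <70% RDI as outcomes".
- **Toxicity:** "We will assess the difference between RT and UC groups in self-reported treatment toxicities in three ways". A is binary, fitted for any of eight symptoms, for each symptom alone and for groups of similar symptoms. B is a count from 0 to 8 of symptoms ever reported as moderate or severe. C is a longitudinal count per cycle.

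The exploratory label is used only for added covariates and for adherence. It is not attached to any analysis above.

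The only significance level is in protocol section 9.3.4: "We have sufficient power (.80) to detect a between arm difference in means of at least .42 standard deviation (s.d.) units", based on a "two-sided t-test, $\alpha=.05$) in Aim 1 analyses of chemotoxicity". That paragraph has already described the chemotoxicity metrics as RDI and number of toxicities. RDI is its worked example: "the minimum detectable difference in mean RDI is 7.3" percentage points.

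**The concern.** When several analyses share primary status and no rule says which one counts, a reader cannot tell what result would make the trial positive. If each is read at 5%, the chance that at least one crosses the line with no true effect exceeds 5%, and the choice of headline can be made after the results are known. This matters more here because participants know whether they are exercising or on the waitlist, and the SAP's toxicity outcome is self-reported. The protocol does not settle the matter: it gives dosing and toxicity equal standing, and its RDI example does not say whether a single agent or ARDI is meant.

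**Working it through.** **1. The plan's own figure.** Inputs: 90 per arm (SAP 2.1, "This study intended to randomize 180 colon cancer patients, with 90 in each treatment arm"), two-sided alpha .05, power .80 and RDI SD 17.3 (protocol 9.3.4). The noncentral t distribution with 178 degrees of freedom gives a detectable difference of 0.420 SD, and 0.420 × 17.3 = 7.27. The stated 0.42 SD and 7.3 are reproduced. This is the power of one comparison.

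**2. Counting the analyses in SAP 2.2.**

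| Analysis | Base count |
|---|---|
| RDI per drug (5-FU, oxaliplatin, capecitabine) | 3 |
| RDI across regimens | 1 |
| Cut points 85% and 70%, combined measure only | 2 |
| A: any symptom | 1 |
| A: each symptom | 8 |
| A: symptom groups (at least one) | 1 |
| B | 1 |
| C | 1 |
| **Total** | **18** |

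The SAP fixes neither the number of agents, nor whether cut points apply per drug, nor the number of symptom groups.

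- *Upper count:* add leucovorin (+1), cut points for four drugs and the combined measure (10 instead of 2, so +8), muscle ache (+1) and the arm-by-time term (+1): 18 + 11 = 29.
- *Lower count:* treat single symptoms and groups as supportive: 18 − 8 − 1 = 9.
- *Narrower families:* four aggregate tests (ARDI, A for any symptom, B, C), or two (one dosing, one toxicity).

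**3. Chance of at least one two-sided p < .05 when the intervention has no effect.** For k independent tests this is 1 − .95^k: k = 2 gives .0975, k = 4 gives .185, k = 18 gives .603. For a common correlation ρ between test statistics it is

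1 − ∫ φ(u) [Φ((1.96 − √ρ·u)/√(1−ρ)) − Φ((−1.96 − √ρ·u)/√(1−ρ))]^k du.

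The documents give no correlations, so ρ is an assumption and a range is shown.

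| k | ρ = 0 | 0.3 | 0.5 | 0.7 | 0.9 |
|---|---|---|---|---|---|
| 2 | 10% | 10% | 9% | 8% | 7% |
| 4 | 19% | 17% | 16% | 13% | 9% |
| 9 | 37% | 33% | 27% | 20% | 12% |
| 18 | 60% | 51% | 40% | 28% | 15% |
| 29 | 77% | 65% | 50% | 33% | 17% |

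Simulation of 18 tests in two blocks (six dosing, twelve toxicity; correlation 0.5–0.8 within blocks and 0.2–0.4 between) gave 28–45%. Counting only false positives that favour exercise, 18 tests give about 37% if independent and 8% at ρ = 0.9.

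**4. Price of controlling error over two tests.** The first step of Holm uses .05/2 = .025. With 90 per arm, the detectable difference is 0.463 SD, and 0.463 × 17.3 = 8.0 points. Power at 0.42 SD falls from .80 to .71. With the actual numbers (SAP 2.1, "we randomized 183 participants, 92 to RT and 91 to UC") it is 0.459 SD, or 7.9 points. The point figures use the RDI SD; no SD is given for ARDI.

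**The case against.** Several parts of the case against stand, and they limit the point.

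- *A reader might infer that the plan tests every analysis at .05.* The SAP states no alpha, confidence level or success rule, and describes toxicity analyses A and B in terms of point and interval estimation. The .05 is borrowed from the protocol's power paragraph. But that paragraph powers a hypothesis test, and unranked intervals allow the same selective headline.
- *A reader might infer that the stated power is invalid because of multiplicity.* It is not. Section 9.3.4 states power per comparison, for RDI and toxicity counts alike, and promises no family-wise rate. Each comparison keeps its own 5%.
- *A reader might quote 60% as the error rate.* That needs independence, which cannot hold: A, B and C reuse the same symptom reports, the cut points are functions of RDI, and ARDI is built from the per-drug values. It is an upper reference for 18 tests, and 18 is itself only one fair count.
- *The RDI example could suggest that RDI leads.* Neither document says so, and it would still leave per-drug RDI, ARDI and the cut points unranked.
- *A rule may exist elsewhere.* A part of the SAP between the end of the section 2.2 text available here and the reference list was not available for this review. The finding is confined to the visible text, which contains no cross-reference to such a rule.

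**Conclusion.** The point holds in a limited form. In the visible text, SAP 2.2 and protocol 9.3.1 place many analyses under the primary endpoints, name no decisive one and give no hierarchy, alpha split or adjustment. Provided each is judged at two-sided .05, the chance of a false-positive primary result exceeds 5% on every count tried: about 7–10% for two tests, 9–19% for four, and about 15–50% for some 18 correlated tests. The conclusion does not depend on the count of 18 or on the assumed correlations; only its size does. The documents do not show that anyone intends to claim success on any single result. They show that nothing in the plan would prevent it.

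**What to change.** Before any arm-level results are seen, and with the date recorded in the SAP:

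1. Name one dosing analysis: the adjusted mean difference in ARDI. Reconcile its definition first, since protocol 4.11 averages over regimens and SAP 1.1 refers to all agents within a regimen.
2. Name one toxicity analysis, B or C, and give the reason. B is closer to the total count in the objective but takes no account of how many cycles a patient reported on. C uses each cycle, but patients who stop early contribute fewer reports.
3. Because the objective does not rank the two domains, control error across the pair with Holm. A pre-stated fixed sequence is an acceptable alternative.
4. Label per-drug RDI, the cut points, the remaining toxicity forms, single symptoms and symptom groups as supportive, with confidence intervals and no claim of significance.

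No data collection changes. Under Holm the first-step detectable difference rises from 0.42 to 0.46 SD (7.3 to 8.0 points if the SD of 17.3 also holds for ARDI). Once one endpoint passes, the other is tested at .05. A fixed sequence keeps 0.42 SD for the first endpoint, but the second is not confirmatory if the first fails. The SAP already reports the final randomised numbers and describes questionnaire completion in the past tense, so timing matters: if arm-level results have been seen, the ranking no longer protects the error rate and should be reported as post hoc.
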